9.2 Setting

9.2.1 Cystic Fibrosis Trust and Cystic Fibrosis Foundation

Patient registries established by the CF Trust and the CF Foundation will be used for this study. These registries are the largest in the geographic regions covered by the current study, representing approximately 9400 of 36,000 patients with CF in the EU and approximately 26,000 of 30,000 patients with CF in the US.^{1,2} The Ivacaftor Long-term Safety Study is an analysis of data collected in these patient registries. These registries are disease registries of observational cohort study design.

The CF Trust Patient Registry is an anonymised database of all those with CF in the UK. This database is maintained by the CF Trust. It is an invaluable tool that is used by the CF Trust to identify patterns and anomalies in CF care and outcomes across the UK.¹⁹

The CF Foundation Patient Registry tracks the treatments and health of people with CF across the US. Information is collected every year on patients who receive care at CF Foundation-accredited care centres and agree to participate in the registry.²

In both registries, all patients participate in standard encounter-based data collection including annual assessments for death, organ transplantation, hospitalisations, complications, pulmonary exacerbations, respiratory microbiology, pregnancy, and pulmonary function. Investigators at CF care centres enter data for their enrolled patients with CF into the registry databases. In both registries, investigators are physicians at certified CF care centres. Data collection forms were developed to capture pertinent data related to CF and the medical care of patients with CF. Changes to data collection forms have been incorporated over the years using a process where changes requested by investigators are reviewed and approved by the governing committee for each registry. The data elements collected are provided in standard terms for diagnoses and treatments and are considered adjudicated diagnoses.

Efforts have been made to provide consistency of care to patients with CF throughout the world. These efforts include treatment guidelines created and maintained by the European Cystic Fibrosis Society (ECFS) and the CF Foundation.^{20,21} Therefore, we are confident that the patient registries in the UK and the US are representative of patients with CF globally.

9.2.2 Other Patient Registries

At the request of the Pharmacovigilance Risk Assessment Committee, other EU patient registries were considered for this study. A feasibility assessment for the inclusion of these registries is provided in Annex 3: Additional Information.

9.2.3 Study Cohorts

Patients from the patient registries will be categorised into 6 cohorts.

1. The Ivacaftor Cohort will include all ivacaftor-treated patients enrolled in the CF Trust or CF Foundation patient registries, regardless of age, *CFTR* genotype, or pulmonary function.

2. The Comparator Cohort will include patients who are not receiving and have never received ivacaftor and are a match on age group, *CFTR* genotype class, and sex to patients in the Ivacaftor Cohort. Based on the mechanism of action of ivacaftor and the availability of genetic testing, it is expected that most patients with *G551D-CFTR* mutation will be exposed to ivacaftor during the study period, making it challenging to identify a comparator cohort of patients with CF with the *G551D-CFTR* mutation who are not exposed to ivacaftor. Therefore, patients in the Comparator Cohort will be matched on *CFTR* genotype class based on the functional classification of *CFTR* alleles.^{14,22}
3. The Historical Cohort will include patients who have the *G551D-CFTR* mutation, were enrolled in the patient registries in 2008 (before ivacaftor was available in clinical studies and commercially in the UK and the US), and have no evidence of exposure to ivacaftor.
4. The Ivacaftor Pregnancy Study Cohort will include all female patients 13 years of age or older who were enrolled in the patient registries and were treated with ivacaftor.
5. The Comparator Pregnancy Study Cohort will include female patients who are not receiving and have never received ivacaftor and are a match on *CFTR* genotype class to patients in the Ivacaftor Pregnancy Cohort.
6. The Drug Utilisation Cohort will include all patients who were enrolled in the patient registries with evidence of ivacaftor exposure.

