9.1.2.3 Historical Cohort

Inclusion Criteria

1. Patients with CF in the CF Trust or the CF Foundation patient registries
2. Patients with the *G551D-CFTR* mutation
3. Patients with no evidence of ivacaftor exposure before ivacaftor was available commercially

Exclusion Criterion

1. Participation in an interventional study during the analysis period (if available)

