The Class III *CFTR* mutations include *G551D*, *G178R*, *S549N*, *S549R*, *G551S*, *G970R*, *G1244E*, *S1251N*, *S1255P*, *G1349D*, and *R560T* (see also RMP).¹⁴ Because of the low prevalence of Class III mutations (<5% overall with approximately 1% representing non-*G551D* mutations), it will not be possible to match patients with the *G551D* mutation to patients with other Class III mutations. The following matching scheme for genotype will be implemented.

- Any Class III *CFTR* allele will be matched to *F508del*, a mutation in a different class (Class II) but of similar phenotype (similar sweat chloride levels, FEV₁, forced vital capacity, height, weight, pancreatic sufficiency, and incidence of *Pseudomonas aeruginosa* colonisation).^{14,22} For example, a patient with *CFTR* alleles of *G551D/F508del* will be matched to a patient with *CFTR* alleles of *F508del/F508del*.
- Alleles in *CFTR* Classes I and II will be matched to Class I or II; alleles in *CFTR* Classes IV and V will be match to Class IV or V.

This scheme will allow for patients with a second allele associated with less severe phenotype (e.g., Class IV or V) to be matched to a patient with a similar genotype and not a more severe class (e.g., Class I to III). Patients with an allele of unknown genotype (meaning mutation has not yet been identified) or a mutation of unknown mutation class will be matched to *F508del*.

The genotype matching algorithm is provided in Figure 1.

Figure 1 Genotype Matching Algorithm

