9.2.5 Other Matching Considerations

Given the limited size of the CF population, the Comparator and Comparator Pregnancy Cohorts will not be matched for other measures of disease severity (e.g., percent predicted FEV₁, *Pseudomonas aeruginosa* infection) due to concerns about availability of adequate patients for matching. However, measures of disease severity will be included as stratification variables and as covariates for adjustment, as necessary.

The Historical Cohort will include patients with a *G551D-CFTR* mutation who were in the patient registries in 2008. These patients were chosen because they represent the best match to ivacaftor-treated patients in 2012 and later because they match the indicated patient population based on the approved product labelling. The Historical Cohort will include patients of all ages and will be stratified to identify outcomes for patients younger than 6 years of age (for the potential off-label population). The year 2008 was chosen because starting in 2009, ivacaftor clinical studies were actively enrolling in the UK and US. A 1-year window was selected to match the window for safety outcome analysis in the Ivacaftor and Comparator Cohorts. The Historical Cohort will be analysed once for Objectives 1 and 2 for all stratification variables. If additional analyses are identified during the conduct of the study, the Historical Cohort will be available for analysis.

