9.3.4 Statistical Analyses

Data analyses will be performed by the CF Trust and CF Foundation to meet the study objectives. The results of the annual analyses will be reported in the study report.

The primary objectives of this study are to evaluate long-term safety, pregnancy outcomes, drug utilisation, and CF disease progression in patients treated with ivacaftor. Descriptive statistics will be calculated for all endpoints. All safety, pregnancy, and CF disease progression endpoints will be compared between the Ivacaftor and Comparator Cohorts or between the Ivacaftor Pregnancy and Comparator Pregnancy Cohorts. Safety and pregnancy outcomes will also be described for the Historical Cohort. Annual incidence rates will be calculated for safety outcomes (Objective 1). Crude relative risks or risk difference with 95% confidence intervals will be calculated for some outcomes, as appropriate. Statistical modelling with adjustment for confounders and effect modifiers will be conducted, as possible, due to the likely sparse data. Identification of confounders and effect modifiers will be performed using stratified analyses. Each annual report will include the patient data from the previous calendar year (e.g., annual cross-sectional analysis). Longitudinal analyses will be included, as appropriate, in the final report.

This section presents a summary of the planned statistical analyses for this study (see [Stand-alone Document 4](#) listed in Annex 1. List of Stand-alone Documents). A detailed

analysis plan will be presented in a statistical analysis plan. A summary of the comparisons to be made for each objective is provided in Table 5.

Table 5 Comparisons by Primary Objective

Objective	Setting	Cohorts Included	Comparisons
1. To evaluate the long-term safety of ivacaftor in patients with CF	UK, US	Ivacaftor; Comparator; Historical	
 Comparison of long-term safety between the Ivacaftor Cohort (ivacaftor-treated patients) and the Comparator Cohort (concurrent nonexposed patients) to include relative risks or risk differences Descriptive statistics for the Historical Cohort (historical nonexposed patients) will be available for comparison to the Ivacaftor Cohort (ivacaftor-treated patients). Comparisons to be based on 95% confidence intervals.

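### Table 5 compares a G551D-only 2008 cohort with treated patients of any genotype; the historical comparison should be limited to treated G551D patients

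*Protocol*

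**What the plan says.** The treated side is open to every genotype. Section 9.2.3 defines the Ivacaftor Cohort as "all ivacaftor-treated patients enrolled in the CF Trust or CF Foundation patient registries, regardless of age, *CFTR* genotype, or pulmonary function", and the criteria in Section 9.1.2.1 add no genotype condition. The Ivacaftor Pregnancy Study Cohort (Section 9.1.2.4) has none either.

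The historical side is closed. Inclusion criterion 2 in Section 9.1.2.3 reads "Patients with the *G551D-CFTR* mutation", and Section 9.2.3 repeats it: "The Historical Cohort will include patients who have the *G551D-CFTR* mutation, were enrolled in the patient registries in 2008". Section 9.2.5 defends these patients as the best match to treated patients because "they match the indicated patient population based on the approved product labelling".

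Table 5 (Section 9.3.4) then joins the two. For Objective 1, descriptive statistics for the Historical Cohort "will be available for comparison to the Ivacaftor Cohort (ivacaftor-treated patients"), and it adds: "Comparisons to be based on 95% confidence intervals". Objective 2 has the same arrangement with the Ivacaftor Pregnancy Study Cohort. Neither row limits the treated side to G551D.

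**The concern.** The reason given for the Historical Cohort is that it fits the label, but the cohort it is set against need not fit the label. Section 8.2.3 names two groups of treated patients outside it by genotype: Class III without G551D, and non-Class III. Section 9.2.5 deals with off-label age on the historical side through a stratum under 6 years. It has no counterpart for off-label genotype in this comparison. The Historical Cohort limitations in Section 9.9 name changed care, a different disease state and changed data fields, but not genotype mix.

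The contrast has some value of its own. Section 9.2.3 expects few untreated G551D patients during the study, and Section 9.2.4 matches Class III alleles to F508del in the concurrent comparison. The 2008 cohort is thus the plan's one defined untreated G551D reference. Mixing genotypes on the treated side gives away part of that advantage, and a difference due to mix could be read as harm or benefit.

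**Working it through.** **Plan's own figures.** The protocol gives no size or power figure for the historical comparison. Table 6 concerns the Ivacaftor and Comparator Cohorts. It reproduces (at relative risk 2, exact one-sided Fisher power is 0.386 and 0.706, against 0.393 and 0.703 stated) but has no bearing here beyond its inputs.

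**Inputs.** From Section 9.5: death rate 103/9,385 = 0.011; N = 432 (UK) and 1,035 (US). Assumed, because the documents are silent: f, the share of treated patients without G551D; k, their event rate divided by that of G551D patients; and a common outcome with a 35% rate.

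**Formula.** Let r be the event rate in G551D patients, and suppose no drug effect and no other difference between the cohorts. The treated rate is (1 − f)r + fkr, so the treated-to-historical ratio is 1 + f(k − 1).

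| f | k = 0.5 | k = 2 |
|---|---|---|
| 1% | 0.995 | 1.01 |
| 5% | 0.975 | 1.05 |
| 10% | 0.95 | 1.10 |
| 20% | 0.90 | 1.20 |

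**Against sampling error.** Take equal N in both cohorts, historical rate b, treated rate p = b[1 + f(k − 1)], and z = (p − b)/√{[p(1 − p) + b(1 − b)]/N}.

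- Death, b = 0.011, f = 10%, N = 1,035. With k = 0.5, p = 0.01045 and z = −0.12. With k = 2, p = 0.0121 and z = 0.0011/0.0047 = 0.23. Even at f = 40% with k = 0.5, z is only −0.51.
- Common outcome, b = 0.35, k = 0.5. At f = 10%, 20% and 30%, z is −0.84, −1.69 and −2.56 for N = 1,035, and −0.54, −1.09 and −1.65 for N = 432.
- Common outcome, k = 2. At f = 10%, p = 0.385 and z is 1.65 (N = 1,035) or 1.07 (N = 432). At f = 20%, p = 0.42 and z is 3.28 or 2.12.

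Up to f = 10%, then, the shift stays below 1.96 standard errors over the whole assumed range of k. For a common outcome in the US registry it passes that level between f = 20% and 30% if k = 0.5, and between 10% and 20% if k = 2.

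**What stratification does.** Section 9.3.4.1 stratifies safety outcomes by CFTR genotype class, and Section 9.2.5 analyses the Historical Cohort for all stratification variables. Treated patients with no Class III allele can therefore be set apart. Section 9.2.4 lists G551D with ten other mutations in Class III, so a treated Class III stratum still mixes G551D with the rest. For pregnancy, Section 9.3.4.2 lists outcome, age and duration of exposure, but not genotype.

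**After restriction to treated G551D patients.** f = 0, so the ratio is 1.00 for any k.

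**The case against.** The strongest reply is that little depends on this. The study is descriptive and meant to generate hypotheses (Section 8.3). The main contrast is with the concurrent Comparator Cohort, which is matched on genotype class and untouched by the point. Class stratification removes treated patients without a Class III allele from the stratified safety reading. Section 9.2.4 treats any Class III allele as similar in phenotype to F508del, which implies k near 1 within Class III. The statistical analysis plan, not at hand, might split Class III by G551D. All of this stands and keeps the point small. It does not remove it: the protocol itself fixes the unrestricted pairing in Table 5, the unstratified totals remain mixed, and the pregnancy analysis lists no genotype stratum.

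A reader might infer two stronger points that the documents do not support.

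- *Drift over the five data years against a fixed reference.* Section 9.2.5 has the Historical Cohort analysed once, and Table 2 and Section 9.2.6 place it in the first yearly report. Further use is left open, but no repeated treated-versus-2008 contrast is scheduled.
- *A fifth of treated Class III patients lacking G551D.* Section 9.2.4 puts Class III prevalence at "<5% overall with approximately 1% representing non-*G551D* mutations". Read as patients, 1% of 26,000 is 260 in the US, and 260/(1,035 + 260) = 20%. That needs every such patient to be treated off-label. The same reading in the UK gives 94 + 432 = 526 of 9,385, or 5.6%, which contradicts the stated ceiling of 5%. The base of the percentage is therefore unclear, and it cannot supply f.

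**Conclusion.** The mismatch is in the current text: a G551D-only reference justified by the label is compared, on 95% confidence intervals, with treated cohorts that have no genotype limit. It can shift the historical contrast for Objectives 1 and 2 without any drug effect. The size is illustrative only, since it rests on assumed f and k and on the cohorts being otherwise alike: a ratio of 0.975 to 1.05 at f = 5% and 0.95 to 1.10 at f = 10% for k from 0.5 to 2, and negligible for death. The effect would be distinguishable from chance only for common outcomes at off-label shares that the documents give no ground to expect. This is a minor point, worth making because the repair is cheap.

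**What to change.** In Table 5 (Objectives 1 and 2) and Section 9.2.5, state: *Comparisons with the Historical Cohort use only ivacaftor-treated patients with at least one G551D allele. Treated patients without a G551D allele are tabulated separately and are not compared with the Historical Cohort.* Add genotype mix to the Historical Cohort limitations in Section 9.9. Keep the any-genotype Ivacaftor Cohort for the concurrent comparison.

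No new data are needed, because both registries define genotype for each allele (Sections 9.3.1.3 and 9.3.2.3); the change is one filter in the tables. The cost is that treated patients without G551D leave this contrast. The standard error on the treated side grows by about 1/√(1 − f): 2.6% at f = 5% and 5.4% at f = 10%. The interval for the contrast widens by less, since the historical side is unchanged. The documents do not give the actual share.

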9.2.4 Comparator Matching

For analyses of safety outcomes and CF disease progression (Objectives 1 and 4), patients in the Comparator Cohort will be matched to patients in the Ivacaftor Cohort on age group, then *CFTR* genotype class, and then, whenever possible, sex, to account for differences in health outcomes during the progression of CF and known differences in health outcomes for male and female patients.²³⁻²⁷

For analyses of pregnancy outcomes (Objective 2), patients in the Comparator Pregnancy Study Cohort (female patients only) will be matched to patients in the Ivacaftor Pregnancy Study Cohort on *CFTR* genotype class; no other matching criterion is used in order to maximise the number of potential matches for an event (pregnancy) expected to have low incidence compared to other safety outcomes.

Age

Age matches will be made based on an age bracket within specific age group categories.

- Patients 0 to 11 years of age (inclusive) will have a bracket of ± 2 years.
- Patients 12 to 20 years of age (inclusive) will have a bracket of ± 2 years.
- Patients older than 20 years of age will have a bracket of ± 5 years.
- Age group categories will be 0 to 2, 3 to 5, 6 to 8, 9 to 12, 13 to 17, 18 to 20, 21 to 25, 26 to 30, 31 to 35, 36 to 40, and >40 years.

For example, a 16-year-old Ivacaftor Cohort patient will be matched to patients in the Comparator Cohort within the bracket of ± 2 years of age (i.e., 14 to 18 years of age), as

limited by the age group category of 13 to 17 years of age (i.e., final age match to patients 14 to 17 years of age). A 21-year-old Ivacaftor Cohort patient will be matched to patients in the Comparator Cohort within the bracket of ± 5 years of age (i.e., 16 to 26 years of age), as limited by the age group category of 21 to 25 years of age (i.e., final age match to patients 21 to 25 years of age).

Age group categories may be collapsed to increase matching when nonexposed patients are not available for matching. These age groups were chosen based on the age-related decline in pulmonary function in patients with CF.^{28,29}

CFTR genotype class

[figure not shown]
The Class III *CFTR* mutations include *G551D*, *G178R*, *S549N*, *S549R*, *G551S*, *G970R*, *G1244E*, *S1251N*, *S1255P*, *G1349D*, and *R560T* (see also RMP).¹⁴ Because of the low prevalence of Class III mutations (<5% overall with approximately 1% representing non-*G551D* mutations), it will not be possible to match patients with the *G551D* mutation to patients with other Class III mutations. The following matching scheme for genotype will be implemented.

- Any Class III *CFTR* allele will be matched to *F508del*, a mutation in a different class (Class II) but of similar phenotype (similar sweat chloride levels, FEV₁, forced vital capacity, height, weight, pancreatic sufficiency, and incidence of *Pseudomonas aeruginosa* colonisation).^{14,22} For example, a patient with *CFTR* alleles of *G551D/F508del* will be matched to a patient with *CFTR* alleles of *F508del/F508del*.
- Alleles in *CFTR* Classes I and II will be matched to Class I or II; alleles in *CFTR* Classes IV and V will be match to Class IV or V.

This scheme will allow for patients with a second allele associated with less severe phenotype (e.g., Class IV or V) to be matched to a patient with a similar genotype and not a more severe class (e.g., Class I to III). Patients with an allele of unknown genotype (meaning mutation has not yet been identified) or a mutation of unknown mutation class will be matched to *F508del*.

The genotype matching algorithm is provided in Figure 1.

Figure 1 Genotype Matching Algorithm

9.2.5 Other Matching Considerations

Given the limited size of the CF population, the Comparator and Comparator Pregnancy Cohorts will not be matched for other measures of disease severity (e.g., percent predicted FEV₁, *Pseudomonas aeruginosa* infection) due to concerns about availability of adequate patients for matching. However, measures of disease severity will be included as stratification variables and as covariates for adjustment, as necessary.

The Historical Cohort will include patients with a *G551D-CFTR* mutation who were in the patient registries in 2008. These patients were chosen because they represent the best match to ivacaftor-treated patients in 2012 and later because they match the indicated patient population based on the approved product labelling. The Historical Cohort will include patients of all ages and will be stratified to identify outcomes for patients younger than 6 years of age (for the potential off-label population). The year 2008 was chosen because starting in 2009, ivacaftor clinical studies were actively enrolling in the UK and US. A 1-year window was selected to match the window for safety outcome analysis in the Ivacaftor and Comparator Cohorts. The Historical Cohort will be analysed once for Objectives 1 and 2 for all stratification variables. If additional analyses are identified during the conduct of the study, the Historical Cohort will be available for analysis.

9.2.6 Annual Reporting

To meet the study objectives, data for outcomes will be analysed separately for each registry for 5 years. All enrolled patients exposed to ivacaftor will be included in the Ivacaftor Cohort, and patients not exposed to ivacaftor and matched for age group, *CFTR* mutation class, and sex, as appropriate, will be included in the Comparator Cohort in the study analyses in each annual report. Each annual report will include the data collected during the previous calendar year. Longitudinal analyses will be included in the final report. The

Historical Cohort will provide an estimate of rates for variables supporting Objectives 1 and 2 and be included in the first yearly report.

9.3 Variables

All variables for study endpoints are collected in prespecified data collection forms. For example, specific diagnoses are captured as data elements rather than as a collection of information from which a diagnosis would be made. Adjudication is done by the governing committees of the patient registries. Investigators (physicians with expertise in CF) from certified CF centres complete the forms according to the data guidelines and indicate the specified diagnoses for patients. Because verbatim terms are not reported and forms contain adjudicated diagnoses, the data are inherently coded. Each registry employs its own data entry guideline rather than use external coding dictionaries.

The CF Trust and CF Foundation patient registries employ data collection instructions and rigorous data cleaning procedures to provide robust data sets for the analysis of ivacaftor safety, drug utilisation, and CF disease progression. The principal investigators of this protocol are both physicians with expertise in CF, familiar with the current standards for treating patients with CF, as well as the data quality process of their respective registries. Therefore, an external expert committee for validation of diagnoses is not planned.

The CF Trust and CF Foundation independently determine the data to be collected; thus, the specific variables included in the analyses for this study are not necessarily identical. Types of variables important for this analysis include exposure, outcomes, and stratification variables. Stratification variables will be explored to identify confounders and effect modifiers. Data are collected for each patient registry; therefore, variables are described separately (Sections 9.3.1 and 9.3.2). Table 4 provides a comparison of the variables to be collected.

Table 4 Comparison of Variables Collected by the Patient Registries

Variables	CF Trust (UK)	CF Foundation (US)
Exposure	start/stop (reason)	yes (150 mg/other)/no
Prior ivacaftor exposure	Derived based on start date before January 2013	Derived based on ivacaftor exposure in 2012
Death	date; cause (respiratory/ cardiorespiratory, liver disease, trauma, suicide, transplant-related, other)	date; cause (respiratory/ cardiorespiratory, liver disease, trauma, suicide, transplant-related, other, unknown)
Organ transplantation	yes (lung, other)/no	yes (lung, liver, kidney, other)/no
Hospitalisation	start date of hospitalisation for pulmonary exacerbation	start date (any hospitalisation); reason (pulmonary exacerbation, pulmonary complication, GI complication, transplant-related, sinus infection, non-transplant surgery, other)
CF complications	see Section 9.3.1.2	see Section 9.3.2.2
Pulmonary exacerbations and respiratory microbiology ^a	yes/no; respiratory microbiology	yes/no; respiratory microbiology

Table 4 Comparison of Variables Collected by the Patient Registries

Variables	CF Trust (UK)	CF Foundation (US)
Pregnancy	pregnancy occurrence/outcome/undelivered/unknown; gestational age; presence of congenital anomalies at birth; only for female patients 13 years of age and older	pregnancy occurrence/outcome/undelivered/unknown; only for female patients
Serious safety outcomes	combination of death, organ transplantations, hospitalisations, and selected CF complications	combination of death, organ transplantations, hospitalisations, and selected CF complications
Pulmonary function tests ^b	FEV ₁ (L), best FEV ₁ (L), FVC (L), FEF _{25%-75%} (L) during last period, unable to perform test, not done	FEV ₁ (L), FVC (L), FEF _{25%-75%} (L), unable to perform test
Cardiac disease	as reported in CF complication	as reported in reason for hospitalisation or CF complications
Hepatic impairment	reported as liver disease with portal hypertension	reported as liver disease with complications

CF: cystic fibrosis; FEF_{25%-75%}: forced midexpiratory flow; FEV₁: forced expiratory volume in 1 second; FVC: forced vital capacity; GI: gastrointestinal; UK: United Kingdom; US: United States.

^a Whilst the specific respiratory microbiology variables collected by the CF Trust and the CF Foundation differ, efforts will be made to create general categories for the analyses. Details will be provided in the statistical analysis plan.

^b Percent predicted FEV₁ will be calculated based on the equations of Hankinson et al.³⁰ or Wang et al.³¹ The Hankinson standard will be used for male patients 18 years and older and female patients 16 years and older. The Wang standard will be used for male patients aged 6 to 17 years and for female patients aged 6 to 15 years.

